2.2 Study Design

2.2.1 Overview

This is an open-label, randomized, parallel-group multicenter study designed to evaluate the efficacy of the digital therapeutic OXD01 combined with SL BUP/NAL SOC background therapy compared to SL BUP/NAL alone to change opioid use patterns in subjects with opioid use disorder (OUD).

The study will include a screening visit and a randomization visit, followed by 24 weeks of study treatment during which the subject will participate in 24 study visits (11 evaluation visits plus 13 visits to perform only a urine drug screen (UDS) and collect a subject self-report of drug use, *Figure 1*).

[figure not shown]
The screening visit will identify opioid dependent adults seeking MAT for moderate-to-severe OUD. Subjects who have received MAT for OUD within 14 days or those with a diagnosis of moderate to severe substance use disorder involving psychoactive substances other than opioids will be excluded.

Eligible subjects will be randomized with a 1:1 fashion into one of two treatment (SL BUP/NAL SOC background therapy or SL BUP/NAL + OXD01 digital therapy). Subjects in both groups will receive the assigned treatment for 24 weeks.

On study Day 1 all subjects will have been stabilized on SL BUP/NAL. Subjects randomized to BUP/NAL plus OXD01 digital therapy will use the OXD01 application as non-pharmacologic treatment for their OUD. OXD01 is a web-based software platform that can be used on a mobile phone, tablet, or computer with a compatible browser such as Google Chrome, Mozilla Firefox, Internet Explorer, or Safari.

Subjects will be scheduled for evaluation visits, which will include a UDS and a self-report of drug use, weekly during the first four weeks of treatment, every other week from weeks 5 through 12, and monthly through 24 weeks. Subjects will also return to the site for a UDS and a self-report of drug use each week between the evaluation visits.

Figure 1. Study schema

R – randomization; SL BUP/NAL – sublingual buprenorphine/naloxone

*Evaluation visits: Weeks 2-5, 7, 9, 11, 13, 17, 21, 25

*Urine drug screen/drug use interview only: Weeks 6, 8, 10, 12, 14-16, 18-20, 22-24

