3.1.2 Analysis Visits

Scheduled visits will be assigned to analysis visits as recorded on the electronic case report form (eCRF). Unscheduled visits recorded on the eCRF will not be re-assigned and will remain labeled as unscheduled.

Early termination (ET) visits will be assigned to analysis visits according to the following visit windows:

| Analysis Visit | Target Analysis Day | Low Analysis Day | High Analysis Day |
|----------------|---------------------|------------------|-------------------|
| Week 2 | 8 | 2 | 11 |
| Week 3 | 15 | 12 | 18 |
| Week 4 | 22 | 19 | 25 |
| Week 5 | 29 | 26 | 32 |
| Week 6 | 36 | 33 | 39 |
| Week 7 | 43 | 40 | 46 |
| Week 8 | 50 | 47 | 53 |
| Week 9 | 57 | 54 | 60 |
| Week 10 | 64 | 61 | 67 |
| Week 11 | 71 | 68 | 74 |
| Week 12 | 78 | 75 | 81 |
| Week 13 | 85 | 82 | 88 |
| Week 14 | 92 | 89 | 95 |
| Week 15 | 99 | 96 | 102 |
| Week 16 | 106 | 103 | 109 |
| Week 17 | 113 | 110 | 116 |
| Week 18 | 120 | 117 | 123 |
| Week 19 | 127 | 124 | 130 |
| Week 20 | 134 | 131 | 137 |
| Week 21 | 141 | 138 | 144 |
| Week 22 | 148 | 145 | 151 |
| Week 23 | 155 | 152 | 158 |
| Week 24 | 162 | 159 | 165 |
| Week 25 | 169 | 166 | |

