- Proportion of subjects completing the study - A completer is defined as a participant who completed either the UDS or the self-report assessment at the Week 25 visit. The groups will be compared with respect to the proportion of completers using a chi-squared test.
- Clinical global impression - This will be evaluated in two ways
 - Score on the CGI-I scale at week 13 and Week 25
 - Change from baseline in the Clinical Global Impression-Severity score at Week 13 and Week 25

CGI scores will be evaluated using General Linear Model (GLM) methodology with treatment as categorical covariate. If substantial deviations from the model assumptions are observed, then supportive analyses such as non-parametric assessments including a Mann-Whitney U test will be performed.

- Opioid cravings - Change from baseline in the opioid craving score using the Opioid Craving VAS from Week 4 to Week 25. Opioid Craving scores will be evaluated using GLM methodology with treatment as categorical covariate. If substantial deviations from the model assumptions are observed, then supportive analyses such as non-parametric assessments including a Mann-Whitney U test will be performed.
- Use of illicit non-opioid drugs of abuse - The cumulative percentage of subjects with urine drug tests negative for illicit drugs of abuse (excluding opioids) plus self-reports negative for illicit drug use for the period from Week 6 to Week 25 will be evaluated using the Kolmogorov-Smirnoff methodology.
- Number of hospitalizations, emergency department visits, and overdoses, and the ability to resume work, school, or other productive activity. descriptive statistics (count and percentage) will be summarized by treatment.

3.4.3 *Exploratory Analysis*

- Percentage of subjects with longer abstinent – Longer abstinence is defined as a subject having urine drug tests negative for opioids as well as self-reports negative for illicit use of opioids at Week 22 – Week 25. Each subject will be scored as abstinent or non-abstinent and the groups will be compared using a chi-squared test.

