The Quantity-Frequency Index (QFI) is a self-assessment of the frequency and quantity of alcohol consumption over the previous 30 days. The QFI is comprised of the two questions and will be completed on study Day 1 and at the visit on Week 25.

Individual data listings of QFI will be presented for each subject and visit of collection.

3.5.6 *Timeline Followback Method – Drug and Alcohol Use*

The Timeline Followback Method – Drug and Alcohol Use (TLFB) is a self-assessment used to document recent use of opioids, other illicit drugs of abuse, and alcohol. A TLFB assessment will be completed on study Day 1, and at weekly visits while on study treatment. The TLFB is a closed Yes or No question of drug or alcohol use.

Individual data listings of TLFB – drugs and TLFB – alcohol will be presented for each subject and visit of collection, separately.

3.5.7 *Opioid Craving Visual Analog Scale*

Cravings for opioids will be assessed by the subject through the use of a VAS, where 0 mm represents “no cravings” and 100 mm represents “the most intensive craving I have ever had.” The baseline craving VAS assessment will be collected on study Day 1 and at the visit on Weeks 5, 9, 13, 17, 21 and 25.

Individual data listings of opioid craving VAS will be presented for each subject and visit of collection.

3.5.8 *Quick Inventory of Depression Symptoms (Self-Report)*

Symptoms of depression will be assessed by the subject using the Quick Inventory of Depression Symptoms Self-Report (QIDS-SR) at screening and at the visit on Week 25.

Individual data listings of QIDS-SR will be presented for each subject and visit of collection.

3.5.9 *Review Behavioral Health Therapies since The Previous Visit*

Subjects in behavioral health therapies since the previous visit, including 12-step programs, will be recorded at the visits on Weeks 1-5, 7, 9, 11, 13, 17, and 21 in eCRF.

Individual data listings of behavioral health since previous visit will be presented for each subject and visit of collection.

3.5.10 *Clinical Global Impression*

Clinical Global Impression (Severity) – Severity of opioid dependence will be assessed by the Investigator on study Day 1 and at the visit on Week 13 and Week 25 using the assessment scale (rate from 0 to 7).

Clinical Global Impression (Improvement) – Improvement in severity of opioid dependence from baseline (study Day 1) will be assessed by the Investigator at the visit on Week 13 and Week 25 using the assessment scale (rate from 0 to 7).

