2. Concomitant medications ongoing on Day 1 will be recorded.
3. As soon as the subject is clinically stable on SL BUP/NAL with physical withdrawal symptoms managed, and the subject able to fully participate in OXD01 training, but no greater than 14 days from the first dose of SL BUP/NAL induction.

Schedule of Events (Continuous): Weeks 13-25, Early Termination

| Evaluation | Treatment | | | | | | | Early Termination |
|--|-------------------|--------------------------------|--------------------|-----------------------------------|--------------------|----------------------------------|--------------------|-------------------|
| | Week 13 Day 85 | Week 14/15/16 Day 92/99/106 | Week 17 Day 113 | Week 18/19/20 Day 120/127/ 134 | Week 21 Day 141 | Week 22/23/24 Day 148/155/162 | Week 25 Day 169 | |
| Window | ± 1 Day | ± 1 Day | ± 1 Day | ± 1 Day | ± 1 Day | ± 1 Days | ± 1 Day | |
| Informed consent | | | | | | | | |
| Demographics | | | | | | | | |
| Inclusion/exclusion criteria review | | | | | | | | |
| Medical history | | | | | | | | |
| Opioid use history | | | | | | | | |
| Confirm diagnosis - OUD ¹ | | | | | | | | |
| Previous treatments for OUD | | | | | | | | |
| Concomitant medications ² | | | | | | | | |
| Physical examination | | | | | | | | |
| Vital signs | | | | | | | | |
| Urine drug screen | X | X | X | X | X | X | X | |
| QFI | | | | | | | X | X |
| TLFB interview – drugs and alcohol | | | | | | | X | X |
| TLFB interview – drugs | X | X | X | X | X | X | | |
| Review study restrictions with subject | X | | X | | X | | | |
| Randomization – IRS ³ | | | | | | | | |
| OXD01 – subject training ³ | | | | | | | | |
| Opioid craving VAS | X | | X | | X | | X | X |
| QIDS-SR | | | | | | | X | X |
| CGI-S | X | | | | | | X | X |
| CGI-I | X | | | | | | X | X |
| Review behavioral health therapies | X | | X | | X | | X | X |
| MAT compliance assessment/counseling | X | | X | | X | | X | X |
| OXD01 compliance assessment/counseling | X | | X | | X | | X | X |
| End of study interview | | | | | | | X | X |
| Adverse Events | X | X | X | X | X | X | X | X |

OUD – opioid use disorder; QFI – Quantity-Frequency Index; TLFB – timeline followback method; IRS – interactive response system; MAT – medication-assisted treatment; VAS – visual analog scale; QIDS-SR – Quick Inventory of Depression Symptoms, Self-Report; CGI-S/I – clinical global impression severity/improvement

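### A single weekly grid for early-termination visits drops CGI scores in 22 of 24 windows and leaves craving VAS handling undefined; that visit also schedules no urine screen

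*SAP*

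**What the plan says.** - **Windows.** SAP 3.1.2: "Early termination (ET) visits will be assigned to analysis visits according to the following visit windows". One table follows, Week 2 to Week 25, with no distinction by assessment. Its last row reads "Week 25 | 169 | 166" and has no upper limit. Under SAP 3.1.1 the day that places a visit in a window is counted from first use of the device.
- **Schedule of VAS and CGI.** SAP 3.5.7 has craving VAS "collected on study Day 1 and at the visit on Weeks 5, 9, 13, 17, 21 and 25". SAP 3.5.10 has CGI-S on Day 1 and both CGI scales at Weeks 13 and 25. Protocol Table 2 and SAP Appendix A mark VAS, CGI-S and CGI-I in the Early Termination column.
- **Analysis.** SAP 3.4.2 lists "Score on the CGI-I scale at week 13 and Week 25", with CGI-S change at the same two weeks. For craving it lists "Change from baseline in the opioid craving score using the Opioid Craving VAS from Week 4 to Week 25". Both use a general linear model with treatment as the only stated term.
- **Missing data.** SAP 3.4.1 sets urine tests and self-reports to positive after withdrawal, and at missed visits of subjects who complete. No rule covers VAS or CGI.
- **Urine at ET.** In both schedules the Weeks 13-25 row reads "Urine drug screen | X | X | X | X | X | X | X", seven marks for the seven treatment columns, and the Early Termination cell is empty. The TLFB is marked there.

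**The concern.** The weekly grid suits urine and TLFB, which are collected weekly. It does not suit scales collected at two or six time points. An ET CGI on Day 78 becomes a Week 12 score, and Week 12 is not analysed. An ET VAS on Day 64 becomes a Week 10 score, a week in which only early leavers can have one. The craving endpoint begins at Week 4, when no VAS is scheduled, so only subjects terminating on Days 19-25 could have a Week 4 score.

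With no missing-data rule for these scales, the CGI comparison, and the craving comparison if made by visit, rest largely on subjects still attending, although the last status of some early leavers was measured. The trial is open-label and compares retention as an endpoint in its own right, so the arms may well differ in who leaves.

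The urine gap is separate. At the ET visit a negative self-report can be recorded, but no urine result is scheduled to go with it.

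**Working it through.** **1. The plan's own visit count.** SAP 2.2.1 gives "24 study visits (11 evaluation visits plus 13 visits to perform only a urine drug screen". Evaluation weeks 2-5, 7, 9, 11, 13, 17, 21 and 25 make 11; urine/self-report-only weeks 6, 8, 10, 12, 14-16, 18-20 and 22-24 make 13. Together they are exactly Weeks 2-25, so 11 + 13 = 24, matching the 24 windows in SAP 3.1.2.

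**2. Windows without a scheduled score.**
- VAS: 24 - 6 = 18; 18/24 = 75%.
- CGI: 24 - 2 = 22; 22/24 = 92%.

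**3. By day of ET.** Take Days 2-168, which is 167 days.
- VAS weeks cover 5 x 7 + 3 = 38 days (the 3 are Days 166-168). Outside: 129/167 = 77%.
- CGI weeks cover 7 + 3 = 10 days. Outside: 157/167 = 94%.

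The documents give no dropout timing, so the following patterns are assumptions:

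| Assumed timing of ET visits | VAS outside | CGI outside |
|---|---|---|
| Even over Days 2-168 | 77% | 94% |
| Density halving every 28 / 56 / 84 days | 83 / 80 / 79% | 98 / 96 / 95% |
| Density doubling every 56 days | 76% | 92% |
| Only at the 10 evaluation weeks before Week 25 | 5/10 = 50% | 9/10 = 90% |
| Only at all 11 evaluation weeks | 5/11 = 45% | 9/11 = 82% |

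**4. Urine at ET.** Weeks 6-25 give 20 visits, and 80% of 20 is 16. A subject whose ET visit falls in the Week *w* window has *w* - 6 earlier visits in the period, so at best *w* - 6 negatives without an ET screen and *w* - 5 with one. Reaching 16 needs *w* - 5 >= 16, that is *w* >= 21.
- Week 21 window, all earlier visits negative: 15/20 = 75% (failure) without the screen, 16/20 = 80% (success) with a negative one.
- Later windows: the screen matters only if exactly 15 earlier visits were negative.
- SAP 3.4.1 does not clearly cover the ET week itself. If that week is left out of the denominator, 15/19 = 78.9%, still a failure.

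**5. What midpoint windows would recover.** VAS target days are 29, 57, 85, 113, 141 and 169, with midpoints 43, 71, 99, 127 and 155. CGI target days are 85 and 169, with midpoint 127. Suppose a scheduled value takes precedence and every earlier scheduled visit was attended.
- VAS, opening at Day 15: Days 15-168 are mapped, 154 days. Superseded: Days 30-42, 58-70, 86-98, 114-126 and 142-154, 5 x 13 = 65. Used: 89/167 = 53%.
- CGI, opening at Day 43: Days 43-168 are mapped, 126 days. Superseded: Days 86-126, 41. Used: 85/167 = 51%, against 10/167 = 6% under the present grid.

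**The case against.** **Craving VAS.** SAP 3.4.2 names a period for craving, not visits, and the model has no visit term. If all values in Weeks 4-25 are used together, 22 of 24 windows lie inside the period and only Weeks 2-3 fall out (2/24 = 8%). A reader might infer a head count. If 80-160 of the 400 subjects attended ET visits spread evenly, a by-visit analysis would strand 60-120 VAS scores (x 0.75), but the pooled reading only about 7-13 (x 2/24). The documents support neither the attendance figure nor the by-visit reading, and subjects lost to follow-up have no ET visit at all. This objection stands: the VAS statement is conditional.

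**Urine.** A reader might infer that an ET week can never hold a urine result. Urine is scheduled weekly, so a scheduled screen may fall in the same window. A reader might also see the missing urine cell as the reason an ET visit from Day 166 can count as Week 25 completion on the TLFB alone. That follows from the plan's explicit definition of a completer, which accepts either assessment. The 15-versus-16 case is also narrow, and its frequency is unknown. All of this stands.

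**Stakes.** CGI and craving are sixth and seventh in the testing hierarchy, reached only if every earlier test is significant, and ET values still appear in listings. This stands too.

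**Remedy.** Wide windows let an early score stand for a later time point, by up to six weeks for CGI, and precedence leaves many ET scores unused. Excluding off-schedule scores and stating a missing-data method would be equally defensible. That is fair, but the SAP does neither.

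**Conclusion.** The CGI part follows from the text with no assumption: an ET score in 22 of 24 windows (92%) enters no analysis. It remains the large majority of ET scores under every timing pattern tried (82-98%). For VAS, 18 of 24 windows (75%) hold dropouts only if craving is analysed by visit. The share of ET scores affected then runs from 45% to 83% depending on timing, so it is not certain to be most of them. The number of subjects cannot be stated.

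The mapping problem concerns secondary endpoints. A reader might infer that it undermines the primary endpoint, but the weekly grid fits urine and TLFB. The primary endpoint is touched only through the absent ET screen, only from the Week 21 window on, and only when no scheduled screen falls in that window. The windows also cannot be applied literally in the BUP/NAL-alone arm, which has no first day of device use. The plan should be changed on these points; they do not threaten its main conclusion.

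**What to change.** 1. **SAP 3.1.2.** Keep the weekly windows for urine and TLFB. Add ET windows for the other scales:
   - VAS: Days 15-42 to Week 5, 43-70 to Week 9, 71-98 to Week 13, 99-126 to Week 17, 127-154 to Week 21, Day 155 on to Week 25.
   - CGI-S and CGI-I: Days 43-126 to Week 13, Day 127 on to Week 25.
   - A scheduled value in the window takes precedence. Earlier ET values are listed only. A sensitivity analysis excludes ET values more than 14 days from target, which mainly affects CGI.
2. **SAP 3.1.1.** Count analysis day from randomization (Study Day 1) in both arms.
3. **Craving endpoint** (SAP 2.1.2 and 3.4.2, and the matching protocol text). Change Week 4 to Week 5, the first post-baseline VAS.
4. **Both schedules of events.** Mark the urine drug screen in the Early Termination column, for any ET visits still to come.

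Items 1 to 3 cost SAP wording and a second window table, plus matching protocol wording for the craving endpoint, and need no new data. They can be made before database lock. Item 4 costs one table cell and one routine screen at a visit already held. The downside is that ET values further from target are accepted, so the listings should show the actual day. The opening days (15 for VAS, 43 for CGI) are choices to fix in advance.

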3.1.3 Definition of Baseline

Baseline is defined as Study Day 1. Subject with missing baseline value will be considered as missing and will be excluded from the analysis for the change from baseline endpoints.

3.1.4 *Summary Statistics*

In general, categorical data will generally be summarized with counts and percentages of subjects. The denominator used for the percentage calculation will be clearly defined.

Continuous data will generally be summarized with descriptive statistics including n (number of observations), mean, median, standard deviation, minimum, and maximum.

3.1.5 *Hypothesis Testing*

Corresponding with the primary efficacy objective of the study, the primary inference for hypothesis testing is the treatment difference between the combination of SL BUP/NAL SOC background therapy and the digital therapeutic OXD01, and SL BUP/NAL alone to reduce opioid use, as measured by the treatment success rate from Week 6 to Week 25. The hypothesis testing is based on a two-sided test with significance level at 0.05.

3.1.6 *Evaluation of Site Effect*

This is a multicenter study. Sites will not be pooled for any planned inferential analysis.

3.2 Analysis Populations

3.2.1 *Full Analysis (FA) Population*

The primary efficacy analyses will be based on FA Population that consists of all randomized subjects.

3.2.2 *Modified Full Analysis (mFA) Population*

The modified FA Population that consists of randomized subjects who were not considered with any data reliability issues. A sensitivity analysis of the primary endpoint and key secondary endpoints will be performed based on mFA Population.

The mFA Population will exclude the following subjects due to data reliability issues:

- 13 subjects enrolled in Site 25 (##-###, ##-##, ##-##)
- 24 subjects enrolled in Site 35 (##-###, ##-##, ##-##)

3.2.3 *Safety Population*

The Safety analyses will be based on Safety Population that is consistent of all randomized subjects.

3.3 Subject Data and Study Conduct

3.3.1 *Subject Disposition*

Counts and percentages of subjects who were randomized, discontinued early from the study, and completed the study will be summarized by treatment on all randomized subjects (FA Population). Reasons for early discontinuation will also be summarized.

For subjects that discontinued early from study, treatment success by treatment group will be investigated with a Kaplan-Meier survival plot, censored to when the subjects dropped out over the course of the study.

3.3.2 *Protocol Deviations*

Protocol deviations will be identified based on the clinical protocol as described in the Protocol Deviation Plan to align with ISO 14155:2020 (Clinical investigation of medical devices for human subjects – Good Clinical Practice). Protocol deviations will be identified prior to unblinding the database.

Counts and percentages of subjects with major protocol deviations by deviation category will be summarized by treatment based on FA Population.

3.3.3 *Analysis Populations*

Counts and percentages of subjects will be summarized by treatment based on FA Population.

3.3.4 *Demographic and Baseline Characteristics*

The following demographic and baseline characteristics will be summarized:

- Age (years)
- Sex
- Childbearing potential
- Race
- Ethnicity
- Baseline craving Visual Analog Scale (VAS)

Demographic and baseline characteristics will be summarized with descriptive statistics or counts and percentages of subjects as appropriate by treatment based on FA Population.

3.3.5 *Opioid Use History/ Treatment*

A treatment history, including counseling, over the previous 2 years for OUD will be recorded at screening. Opioid use history and treatment including main drug of abuse and primary route used, will be summarized by treatment based on Safety Population.

3.3.6 *Medical History*

Medical history will be coded to system organ class and preferred term using the Medical Dictionary for Regulatory Activities (MedDRA) version 24.0. Counts and percentages of subjects with medical history by system organ class and preferred term will be summarized by treatment based on the Safety Population.

3.3.7 *Concomitant Medications*

Concomitant medications that are ongoing on study Day 1 will be recorded. Additions, deletions, or changes to concomitant medications after Day 1 will not be recorded.

Concomitant medications will be coded to anatomical therapeutic chemical (ATC) class and preferred term using the WHO Drug Dictionary version March 2021G B3. For summary purposes, medications will be considered prior medications if they stopped prior to the first use of study device (Day 1) and concomitant medications if they were taken at any time after the first use of study device (i.e. started prior to Day 1 and were ongoing or started after Day 1).

If a medication has incomplete start or stop dates, dates will be imputed to determine whether a medication should be considered prior or concomitant. If a medication start date is incomplete, the first day of the month will be imputed for missing day and January will be imputed for

missing month. If a medication stop date is incomplete, the last day of the month will be imputed for missing day and December will be imputed for missing month. Incomplete start and stop dates will be listed as collected without imputation.

Counts and percentages of subjects taking concomitant medications by ATC class and a preferred term will be summarized by treatment based on the Safety Population.

3.3.8 *Study Device Compliance*

Dosing instructions will be reviewed and subjects will be interviewed to assess treatment compliance at the following Visits: Weeks 2-5, 7, 9, 11, 13, 17, 21, and 25.

Percent compliance of study device OXD01 will be calculated as the number of OXD01 sessions taken / the number of expected OXD01 sessions taken. Percent compliance to the study device regimen will be summarized based on the Safety Population with descriptive statistics and with counts and percentages of subjects with compliance in the following categories:

- <50%
- 50-80%
- 80-100%
- >100%

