3.4 Efficacy Assessment

Efficacy data will be summarized by randomized treatment based on the FA Population. The primary efficacy endpoint will also be summarized based on the mFA Population.

3.4.1 *Primary Endpoints Analysis*

The primary objective of the study is to determine whether the combination of SL BUP/NAL SOC background therapy and the digital therapeutic OXD01 is superior to SL BUP/NAL alone to reduce opioid use, as measured by the treatment success rate. Treatment success is defined as the subject having $\geq 80\%$ of urine drug tests negative for opioids plus $\geq 80\%$ of self-reports negative for illicit opioid use (from the TLFB interview at the same visit) from Week 6 to Week 25. Each subject will be evaluated as a success or failure for this metric and the proportion of subjects in each group demonstrating $\geq 80\%$ of urine drug tests negative for opioids plus negative self-reports for illicit opioid use (from the TLFB interview) will be tested using chi-squared test. Count and percentage of the subjects with treatment success will be summarized by treatment based on FA Population.

If the subject withdrew the study, then the urine drug tests for opioids and self-reports for illicit opioid use after withdrawal will be imputed as positive. If the subject completed the study with any missing visit, then the urine drug tests for opioids and self-reports for illicit opioid use for the missing visit will be imputed as positive.

Sensitivity analysis 1

As supportive analyses to the primary analysis for the primary endpoint, sub-group analysis using a similar chi-squared test as described above will be repeated for the following factors:

- Percentage of subjects meeting primary endpoint by reported compliance rate or who achieved greater than 80% completion of the visits during Week 6 to Week 25
- Subjects who took the dose of buprenorphine versus retention.
 - Target dose or lower: ≤ 16 mg buprenorphine for Suboxone or equivalent formulation; or ≤ 11.4 mg Zubsolv
 - Higher dose than target dose: > 16 mg buprenorphine for Suboxone or equivalent formulation; or > 11.4 mg Zubsolv
- Subjects who received additional behavioral health services

Sensitivity analysis 2

As supportive analyses, the primary endpoint and key secondary endpoints will be performed using the similar statistical methods based on mFA Population.

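### The Kaplan-Meier plot in SAP 3.3.1 follows an outcome with no event date, among early leavers only, with drop-out as censoring, so it cannot be interpreted and leaves the timing of drop-out by arm unshown

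*SAP*

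**What the plan says.** SAP 3.3.1 (Subject Disposition) first plans a table by arm of how many subjects were randomized, left early and finished, with the reasons for leaving. It then adds the plot, for subjects who left early: "treatment success by treatment group will be investigated with a Kaplan-Meier survival plot, censored to when the subjects dropped out". It gives no event date, no denominator and no rule for visits that did not take place.

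SAP 3.4.1 defines the outcome: "Treatment success is defined as the subject having $\geq 80\%$ of urine drug tests negative for opioids", with a matching condition on self-reports, over Weeks 6 to 25. It is scored once per subject: "Each subject will be evaluated as a success or failure for this metric". For subjects who withdraw, "urine drug tests for opioids and self-reports for illicit opioid use after withdrawal will be imputed as positive". For missed visits in subjects who finish, urine tests and "self-reports for illicit opioid use for the missing visit will be imputed as positive".

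Elsewhere, SAP 3.4.2 compares the arms on the proportion of completers (a urine screen or a self-report at Week 25) with a chi-squared test. No time-to-discontinuation curve is planned in either document.

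**The concern.** A Kaplan-Meier curve needs a dated event, a population at risk from a common origin, and censoring that says nothing about the subject's later chance of the event. This plot has none of the three. Success is a summary over a 20-week window. The plotted group is selected by a post-randomization outcome, so the two arms within it are no longer randomized groups. And drop-out is strongly tied to success under the primary scoring.

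What is at stake is the reading of the primary result. The trial is open-label and only one arm receives the device. Because visits after withdrawal count as positive, leaving early enough settles the primary outcome as failure. A reader will want to know whether, and when, the arms lose subjects at different rates. The only planned time display that involves drop-out uses it as the censoring mark, so it cannot answer that.

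**Working it through.** The plan states no figure for this plot. The one figure tied to treatment success is the sample size in SAP 2.2.4: about 200 per arm for 12% against 25%, 90% power, two-sided 0.05. It reproduces: the continuity-corrected formula gives 201 per arm, and exact Fisher power at 200 per arm is 90.4%. It plays no part below, except that 12% and 25% serve as illustrative success rates.

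**Visits and threshold.** From the visit list under Figure 1 (SAP 2.2.1), Weeks 6 to 25 contain 13 screen-only visits and 7 evaluation visits (Weeks 7, 9, 11, 13, 17, 21, 25): 13 + 7 = 20. The threshold is 0.80 × 20 = 16 negative visits. The 16th visit is Week 6 + 15 = Week 21, target Day 141 in SAP 3.1.2, give or take the one-day visit window.

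**Best possible score by last attended visit**, with later visits imputed positive:

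| Last visit | Visits attended, at most | Highest score | Positive or missed visits allowed |
|---|---|---|---|
| Week 20 | 15 | 15/20 = 75% | certain failure |
| Week 21 | 16 | 16/20 = 80% | 0 |
| Week 22 | 17 | 17/20 = 85% | 1 |
| Week 23 | 18 | 18/20 = 90% | 2 |
| Week 24 | 19 | 19/20 = 95% | 3 |

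The bound is the same whether 80% is applied jointly or separately to urine tests and self-reports, since either way at least 16 negative urine tests are needed. The early termination column of the schedule marks no urine drug screen, so that visit would not supply a missing test.

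**Share of plotted subjects who could have an event.** The documents give no drop-out rate or timing, so this needs an assumption.

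- Last visit spread evenly over Weeks 1 to 24: 4/24 = 16.7% could have an event, so at least 20/24 = 83.3% are censored.
- If, further, 12% to 25% of those late leavers succeed: events are 0.167 × 0.12 = 2.0% to 0.167 × 0.25 = 4.2%, and 96% to 98% are censored.
- Front-loaded drop-out, with weight exp(−ht) on last visit t + 1 (t = 0 to 23): the share able to have an event is 12.1% at h = 0.03 and 4.9% at h = 0.10. Events then run from 0.049 × 0.12 = 0.6% to 0.121 × 0.25 = 3.0%.

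**The two sections side by side.** Take a subject whose last visit is Week 12. SAP 3.4.1 gives at most 7/20 = 35%, a failure. SAP 3.3.1 censors the same subject at drop-out, which leaves later success open and assigns the chances of those who stayed longer.

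**The case against.** The strongest reply is that the Week 21 bound is imported. SAP 3.3.1 does not say that the fixed 20-visit denominator and the positive imputation apply to the plot. A plot that censors at drop-out may be meant to use only visits observed up to then, and on that denominator the 16-visit bound fails. This stands as a limit on the arithmetic. It does not rescue the plot: a running proportion can cross 80% more than once, so the event would still be undated, and the SAP would hold a second, unspecified definition of success.

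It can also be said that the sentence is a clumsy description of a plot of all randomized subjects in which leavers are censored. The wording would then still need correcting, and under the 3.4.1 rules no event could occur before Week 21.

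Four stronger statements might be inferred, and the documents do not support them:

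- That 3.4.1 counts every drop-out as a failure. It imputes only visits after withdrawal, so subjects whose last visit is Week 21 to 24 can still succeed. Events in that period would agree with the primary scoring.
- That retention is not reported. The disposition table, the reasons for leaving and the completer test all report it; only its timing by arm is missing.
- That almost everyone plotted would certainly be censored. That depends on an assumed drop-out pattern and would weaken if most drop-out came after Week 21.
- That the primary result is at risk. No test, error rate or sample size depends on this plot.

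**Conclusion.** The concern holds as a defect in one descriptive display. On the literal text the plot has an undated outcome, a population selected after randomization, and a censoring rule tied to the outcome. Those three points need no assumption about drop-out.

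The size rests on two conditions. If 3.4.1 governs the plot, no event can occur before Week 21, and every leaver with an earlier last visit is censored although 3.4.1 makes that subject a certain failure. If, in addition, last visits are evenly spread over Weeks 1 to 24, at least 83% of the plotted subjects are censored. The practical loss is that no planned display shows when each arm loses subjects. The change is recommended rather than essential, because the primary analysis stands without it.

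**What to change.** Replace the Kaplan-Meier sentence in SAP 3.3.1 with a Kaplan-Meier plot of time from randomization to study discontinuation for any reason, by randomized treatment, in the Full Analysis Population. Censor completers at their Week 25 visit, show numbers at risk, and use the last attended visit as the discontinuation date for subjects lost to follow-up. Drop treatment success as the event; its comparison between arms already has its place in 3.4.1.

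The time origin should be stated as randomization. SAP 3.1.1 counts analysis days from first use of the device, a date that the control arm does not have.

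The cost is SAP wording and one figure. The documents do not say that a separate discontinuation date is recorded, but subjects are randomized on Day 1 and the SAP's listings are sorted by visit date, so the last attended visit should be available for every subject.
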